## 9.5.8.3 Exploratory Endpoints

# 9.5.8.4 Statistical Methods

Observed values and changes from baseline for HAMD17, EPDS, and STAI6 total scores, subscales, and individual items will be summarized by visit. The categorical outcomes of HAMD17 response, HAMD17 remission, and CGI-I will be summarized by visit.

The preferred approach for exploratory analysis of continuous efficacy variables will be mixed model repeated measures (MMRM) but other approaches such as t-tests, analysis of covariance, or non-parametric methods may be used if necessary or more practical. Similarly, the preferred approach for analysis of categorical efficacy variables will be repeated measures (e.g., generalized estimating equations) but other approaches such as chi square or Fisher's exact tests may be used.

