# 4.0 Introduction

This SAP should be read in conjunction with the study protocol and case report form (CRF). This SAP amendment is based on Protocol Version 8.0, Amendment 7 dated 08Oct2018 and CRF dated 09Aug2018. Any further changes to the protocol or CRF may necessitate updates to the SAP.

Analyses presented to the Data Review Committee (DRC), as well as the pharmacokinetic (PK) and neurosteroid analyses, will not be detailed in this SAP.

This SAP supersedes the statistical considerations identified in the protocol; where considerations are substantially different, they will be so identified in Section 4.1. Any post-hoc or unplanned analyses not included in this SAP, or significant changes from the planned analysis in this SAP, will be clearly identified in Section 9.8.2 of the clinical study report (CSR). Changes to planned analyses after database lock do not require an updated SAP but should be included in the CSR.

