### 12.5 Efficacy Analyses

Statistical analysis of efficacy endpoints will primarily be done using the mITT set and will be done only to aid in interpretation as the trial was not powered for inferential hypothesis testing. As such, there will be no adjustments for inflation of type 1 error due to multiplicity.

For efficacy endpoints expressed as continuous variables, summary tables will show continuous summary statistics for each time point of data collection (visit) as well as least squares (LS) means with standard errors (SEs) and associated p-values from mixed model repeated measures (MMRM) analysis. Summary statistics by time point will also be displayed graphically using bar and/or line charts. MMRM models will include fixed effects for treatment, visit, and the treatment-by-visit interaction, and the baseline observation will be included as a covariate. Repeated measurements are made on each subject. Residuals will be evaluated for substantial departure from normality and independent and constant variance. Methods such as data transformation, detecting and assessing the influence of outliers, and alternative analytical approaches (e.g., non-parametric) may be used to address assumption deviations. An unstructured covariance will be the default covariance structure but other structures (e.g., compound symmetry) may be used to evaluate sensitivity to the choice of structure or, if necessary, to achieve convergence. MMRM assumes missing observations are missing at random (MAR); i.e., missingness depends only on variables other than the outcome that are available in the database. Because the MAR assumption is not testable, and because it seems possible that subjects with poorer outcome may be more likely to miss trial assessments, a sensitivity analysis may be done in which all missing data will be imputed. Conservatively, multiple imputation with a pattern-mixture model will be used; specifically, for all subjects with missing observations regardless of treatment assignment, imputation will be based only on subjects randomized to placebo. The imputation method will be fully conditional specification (FCS) regression with 25 imputations. Variables in the imputer's model will be observed values at each time point included in the MMRM analysis, including baseline.

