For efficacy endpoints expressed as categorical (including binary) variables, summary tables will show frequencies and percentages of subjects in each category as well as adjusted event rates with SEs and associated p-values using general estimating equations (GEE). Summary statistics by time point will also be displayed graphically using bar charts. GEE models will include main effects for treatment and visit and an interaction term for treatment-by-visit. Baseline will be included as a covariate where applicable. Unstructured covariance will be specified but alternative structures (e.g., CS) or alternative statistical methods (e.g., chi square tests of association) may be used if GEE convergence cannot be achieved. GEE assumes missing observations are missing completely at random (MCAR); i.e., missingness is independent of all other information whether it was collected or not. A sensitivity analysis based on multiple imputation, as described above, may be done in which FCS logistic regression would be the imputation method.

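### SAP 12.5: the optional placebo-only imputation has too many predictors for one cohort's placebo arm, and the convergence-only exit from GEE can miss 0% or 100% cells (exploratory analyses; minor to moderate)

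*SAP*

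**What the plan says.** **Imputation.** SAP 12.5 says that "a sensitivity analysis may be done in which all missing data will be imputed", because subjects who do worse may be likelier to miss assessments. It uses fully conditional specification regression with 25 imputations. For subjects in either arm, "imputation will be based only on subjects randomized to placebo", and the variables in the imputation model "will be observed values at each time point included in the MMRM analysis, including baseline". Whether donors come from the subject's own cohort or from several is not stated; SAP 12.0 lays out tables by arm within each cohort. For categorical endpoints, a parallel sensitivity analysis "may be done in which FCS logistic regression would be the imputation method".

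**GEE.** For response, remission and CGI-I, "GEE models will include main effects for treatment and visit and an interaction term for treatment-by-visit". Other correlation structures or other methods, with chi square as the example, "may be used if GEE convergence cannot be achieved". Protocol 9.5.8.4 prefers repeated-measures methods but adds that "other approaches such as chi square or Fisher's exact tests may be used", with no such condition. SAP 4.0 states: "This SAP supersedes the statistical considerations identified in the protocol". The same sentence says that substantial differences are listed in SAP 4.1, and 4.1 lists none on categorical methods.

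**The concern.** In a regression imputation, the residual degrees of freedom are the donors observed at that visit minus the coefficients. At 1 to 3 degrees of freedom the model still runs without an error, but its draws are extremely variable. At zero it cannot be fitted as written. This is the one missing-data check that the SAP specifies, so it should be able to inform. Imputing response and remission by a separate logistic model also allows a subject's imputed status to contradict her imputed HAMD17 total.

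In the GEE, an arm with 0% or 100% at a visit has no finite logit. If software nevertheless reports convergence, the SAP's trigger does not operate. The table may then print a meaningless p-value, or no standard error, beside counts such as 0/10 and 1/10.

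**Working it through.** The plan gives no figure of its own here, so the check starts from its schedules.

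**Inputs.** Allocation is 1:1 (SAP 6.1). Cohort 3 was to be completed with 20 subjects (Protocol 1.2.1.4), so about 10 placebo. Cohort 6 is about 10 to 30 (SAP 6.1), so 5 to 15 placebo. Post-baseline HAMD17 visits:
- IV cohorts: +12, +24, +48, +60 and +72 h, Days 11 and 34, which is 7.
- Cohort 6: +6 h, Days 2, 4, 8, 11, 15, 22, 29, 36, 57 and 71, which is 11.

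**Residual degrees of freedom, own-cohort donors, nothing missing.** Coefficients = intercept + baseline + (visits − 1). Residual df = placebo donors − coefficients.

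| Case | Coefficients | Donors | Residual df |
|---|---|---|---|
| Cohort 3, HAMD17 | 1+1+6 = 8 | 10 | 2 |
| Cohort 3, EPDS (3 visits) | 1+1+2 = 4 | 10 | 6 |
| Cohort 6, N=30, HAMD17 | 1+1+10 = 12 | 15 | 3 |
| Cohort 6, N=24, HAMD17 | 12 | 12 | 0 |
| Cohort 6, N=30, data to Day 29 (8 visits) | 1+1+7 = 9 | 15 | 6 |

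Each placebo subject missing the visit removes one more. The binomial chance that none remain, at assumed missingness of 10% and 20%, is 26% and 62% in Cohort 3 (at least 2 of 10 missing), and 18% and 60% in Cohort 6 at N=30 (at least 3 of 15).

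**Error of an imputed value.** Assumed: SD 5 at baseline and 6 to 8 after; AR(1) and exchangeable patterns; correlations 0.6 and 0.85; 4,000 draws per case at the last visit. Entries are the 95th-percentile distance from the true conditional mean, as a multiple of the correct distance.

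| Case | SAP list | Baseline + preceding visit |
|---|---|---|
| Cohort 3, own donors | 6.2–6.5 | 1.6–1.9 |
| Cohort 3, one placebo missing | 18–20 | 1.8–2.0 |
| Cohort 6, N=30 | 4.6–4.8 | 1.4–1.7 |
| Cohort 6, N=30, Day 29 cutoff | 2.5–2.6 | 1.4–1.6 |
| IV cohort, N=30 | 2.2 | 1.3–1.7 |
| 21 pooled IV donors (5 + 6 + 10; the 5 is assumed) | 1.6–1.7 | 1.3–1.5 |

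Repeat runs with separate code gave 5.5–7.0 (SAP list) and 1.6–1.9 (short list) for Cohort 3, and 4.5–4.9 and 1.3–1.7 for Cohort 6 at N=30.

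**Effect on the treatment difference.** Cohort 3, one subject per arm missing at Day 34, correlation 0.85, no true effect, 1,000 datasets per case. The median SE relative to complete data was 3.1–4.6 with the SAP list and own donors, 1.05–1.11 with the short list and own donors, and 1.08–1.15 with the SAP list and pooled donors. The difference moved by more than 3 points in 25–31%, 0% and 0–1% of datasets. In Cohort 6 at N=30, with 3 missing at Day 71 (one of them placebo), the SE ratio was 1.5–1.9 with the SAP list and 1.03–1.08 with the short list.

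**Empty and full cells.** With 10 per arm, the chance of no event in one cell is (1 − p)^10: 60%, 35% and 11% at true rates of 5%, 10% and 20%. Over 7 visits and two arms at N=20, the simulated chance of at least one 0% or 100% cell for remission was 91–96% (rates 5–25%), 67–75% (10–40%) and 16–19% (25–60%). For response it was 44–51% (15–50%) and 9–11% at higher rates. The documents give no event rates, so all of these are assumed.

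**GEE fits** (statsmodels, no true effect, N=20, 7 visits, 150 datasets per scenario, each with such a cell), under the SAP's default unstructured correlation:

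| Scenario | Flagged converged | Affected visits with p<0.001 | SE missing | Fisher p<0.05 |
|---|---|---|---|---|
| Remission 5–25% | 120/150 | 153/265 | 61 | 1 |
| Remission 10–40% | 137/150 | 103/226 | 56 | 10 |
| Response 15–50% | 147/150 | 92/212 | 61 | 19 |

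Under exchangeable correlation all 150 converged in each scenario. In another simulation with different assumed rates, 183 of 183 fits with such a cell were flagged converged, and the SEs were mostly huge or not computable rather than falsely small.

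**The case against.** The case for leaving the text alone has real force.

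- **Optional and exploratory.** Both imputations are permitted rather than required, efficacy is hypothesis-generating, and Protocol 9.4 leaves room for other missing-data work. This stands and limits the severity.
- **Pooling is allowed.** SAP 12.5 asks only that donors be randomized to placebo. A reader might infer that the imputation cannot work in the IV cohorts. The text does not support that: pooling removes most of the problem there, and IV EPDS is usable even with own donors. Pooling cannot serve Cohort 6, because no IV cohort has its Day 8, 15, 22, 29, 57 or 71 assessments.
- **The primary visits.** A reader might infer that the primary comparison is at risk. The simulated shifts are at Days 34 and 71, whereas the 3 to 4 point benchmark in SAP 12.5.1 applies at 60 hours (IV) and Day 29 (Cohort 6). The 60-hour rating is inpatient, so few values should be missing. The large SE would also make the check visibly uninformative rather than falsely reassuring.
- **The GEE trigger sometimes works.** It fired in 30, 13 and 3 of 150 unstructured fits, so it would be wrong to say that it never catches the failure. SAP 12.0 specifies SAS, which was not tested. A missing or huge SE is easily noticed, and raw frequencies appear in the same tables. What stands is that most such fits passed as converged, many of them with p<0.001.
- **Fisher's exact test may still be available.** Since SAP 4.1 lists no change, the protocol's unconditional wording arguably survives. That leaves two texts that read differently, which is a reason to align them.

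**Conclusion.** Two clarifications to SAP 12.5 are warranted, at minor to moderate weight and for exploratory analyses only.

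The degrees-of-freedom counts follow from the documents once own-cohort donors are assumed. In Cohort 6 that assumption is forced for most visits. The problem is serious there with follow-up to Day 71, but mild at N=30 if the data stop at a Day 29 cutoff, which SAP 10.3 would allow. The error multiples and shifts also rest on assumed SDs, correlations and missingness.

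The GEE gap is that the stated exit is tied to a convergence flag rather than to the cells themselves. That a 0% or 100% cell has no finite logit is a property of the model. How often software flags such a fit as converged was seen only in statsmodels, and how often such cells occur depends on event rates that the documents do not give.

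A reader might extend the point to the unstructured MMRM. That does not follow: SAP 12.5 already permits other covariance structures and alternative methods.

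**What to change.** **Imputation.** In SAP 12.5:
- Limit the predictors for HAMD17 and STAI6 to a short list, such as baseline and the preceding visit.
- Name the donor pool: placebo pooled across the IV cohorts for those cohorts, and own placebo for Cohort 6.
- Derive response and remission from the imputed HAMD17 totals in place of a separate logistic imputation.

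**GEE.** Add that where any arm-by-visit cell is 0% or 100%, the endpoint is reported by visit with an exact method, whatever the convergence flag says. This can be a risk difference with an exact confidence interval, or Fisher's exact test. For 0/10 against 1/10, an exact unconditional interval gives a difference of 10 points with a 95% CI of roughly −20 to +45. Align SAP 12.5 with Protocol 9.5.8.4, or list the difference in SAP 4.1.

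**Cost.** SAP wording and modest programming. The short list gives up some earlier-visit information. Pooling assumes that placebo subjects are comparable across the IV cohorts. Exact intervals are wide, and in small cohorts GEE would often be replaced for remission: at N=20, in 67–96% of cases at the low and middle assumed rates.

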# 6.0 Study Design

### 6.1 General Description

This is a Phase 2A, double-blind, placebo-controlled, multiple-dose escalation study consisting of up to 6 cohorts (Cohort 1 to 6).

Approximately 200 women with PPD 18–45 years of age will be screened to randomize up to 100 subjects across up to 6 cohorts, with Cohorts 4 and 5 optional. Approximately 10-30 subjects will be randomized into each cohort. Randomized subjects will receive ganaxolone or matching placebo in a 1:1 ratio. The study will be conducted in the United States at approximately 15 investigative sites.

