#### Table 1. Schedule of Assessments – Cohorts 1-5

Day	Day -14 to -1	Day 0	Day 1	Day 2	Day 3	Day 4	Day 11 (Day 7	Day 34 (Post
	-	-	(Start	-	(End	(Discharge)	Post Discharge)	Discharge
			Infusion in		Infusion			Day 30)
			AM, 0h)		in PM)			
VISIT	Screening	Admission	Infusion	Infusion	Infusion	Discharge	Follow-up	Follow-up
STAI6	Х		Х	Х	Х	Х	Х	Х
Q15 min health checks & pulse ox			throughout					

Specific timepoints for assessments on days +1, +2, +3 and +4: - Cohorts 1-5

PK samples: +12h, +24h, +48h, +72h HAMD17: before start of infusion, +12h, +24h, +48h, +60h, +72h all done by CTNI CGI-I: +12h, +24h, +48h, +60h, +72h CGI-S: before start of infusion EPDS: before start of infusion, +60h STAI6: before start of infusion, +12h, +24h, +48h, +60h, +72h ECG: +12h, +24h, +48h, +72h Vital Signs: (BP/P/p02/RR/Temp): before start of infusion, +4, +8h, +12, +18h, +24h, +32h, +40h, +48h, +56h, +60h, +72h SSS: before start of infusion, +8h, +32h, +56h, +72h CSSRS: before start of infusion, +12h, +36h, +60, +72h Safety laboratory tests and neurosteroid level: +48h Urinalysis drug and pregnancy test: +72h Physical examination: +72h AEs and concomitant medications are collected throughout the inpatient stay.

Q15min health checks are done from the time of admission to the time of discharge. Pulse oximetry (pO2) must be monitored throughout the infusion, including during the night when the subject is sleeping. The subject should be awakened if pulse oximetry falls < 91%.

The following priority order will be in effect when more than 1 assessment is required at a particular time point: 1) HAMD17 2) CGI-I/CGI-S 3) EPDS 4) STAI6 5) SSS 6) CSSRS 7) vital signs 8) ECG 9) safety labs and neurosteroid level 10) PK sample 11) neurosteroid level 12) urinalysis drug screen and pregnancy test 13) physical examination

Day 11 and Day 34 visits have visit windows of ± 3 and ± 5 days, respectively

#### Table 2. Schedule of Assessments - Cohort 6

Day	Day -14 to -1	Day 0 Admission	Day 1	Day 1°	Day 2f	Days 3 & 5	Day 4	Day 8	Days 10 & 13	Day 11	Day 15	Day 22	Day 29	Day 36	Day 57	Day 71
VISIT	Screenin g		Baseline	Post-BL	Discharge & Outpatient	Safety call	V3 HAMD Call	V4 outpt	Safety call	V5 HAMD Call	V6 outpt	V7 outpt	V8 outpt	l st Follow- up	2 nd Follow- up	3rd Follow- up
Informed consent	X															
Demographics, Medical History	X		33								23 - 23 					
MINI neuropsychiatric interview	X															
Inclusion/Exclusion criteria	X	X														

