### 7.1.5 Clinical Global Impression-Improvement (CGI-I)

The Clinical Global Impression – Improvement scale (CGI-I) is a 7-point scale that asks the clinician to assess how much the subject's illness has improved or worsened relative to a baseline state at the beginning of the intervention. It is rated as: 1, very much improved; 2, much improved; 3, minimally improved; 4, no change; 5, minimally worse; 6, much worse; or 7, very much worse.

CGI-I responses will be assessed at each post-baseline in-person visit.

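### The SAP does not say how the ordered 7-level CGI-I enters its GEE, and the only alternative tests named ignore the order

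*SAP*

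**What the plan says.** SAP 7.1.5 describes an ordered clinician rating: "It is rated as: 1, very much improved; 2, much improved; 3, minimally improved; 4, no change", continuing down to 7, very much worse. SAP 12.5.2 lists the rating itself as a secondary endpoint and defines no cut. Protocol 9.5.8.4 groups it with two binary outcomes: "The categorical outcomes of HAMD17 response, HAMD17 remission, and CGI-I will be summarized by visit".

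For categorical endpoints, SAP 12.5 states that "GEE models will include main effects for treatment and visit and an interaction term for treatment-by-visit" and asks for an unstructured covariance. It promises adjusted event rates but does not define an event for a seven-level rating. If the fit fails, other covariance structures are allowed, or "alternative statistical methods (e.g., chi square tests of association) may be used if GEE convergence cannot be achieved". Protocol 9.5.8.4 says that "other approaches such as chi square or Fisher's exact tests may be used". Both documents mention non-parametric methods only for continuous endpoints.

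On size, SAP 6.1 says "Approximately 10-30 subjects will be randomized into each cohort" in a 1:1 ratio, and SAP 12.0 tabulates by treatment within cohort. Protocol 1.2.1.4 mentions 12 women reviewed in Cohort 2 and a recommended 20 for Cohort 3.

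**The concern.** Two gaps meet here. The model form for CGI-I is left open among options that differ greatly in size and in whether they use the ordering. And the tests named for the case where the model fails treat the seven ratings as unordered labels, on tables far too sparse for the chi-square approximation.

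CGI-I is the only clinician-rated global outcome after baseline, since CGI-S stops on Day 1. The protocol says the results will inform the choice of dose and regimen. With 5-15 women per arm, an order-blind test can miss a consistent movement towards better ratings. Leaving the form unstated also means that the method for a secondary endpoint may be settled only once the fit has been seen.

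**Working it through.** **Inputs from the documents.** Seven levels. Cohorts 1-5 have five inpatient ratings ("CGI-I: +12h, +24h, +48h, +60h, +72h") plus Day 11 and Day 34, so V = 7. For Cohort 6, "CGI-I responses will be assessed at each post-baseline in-person visit" and the schedule give +6h and Days 2, 8, 15, 22, 29, 36, 57 and 71, so V = 9. A cohort of 10-30 gives 5-15 per arm. The documents state no alpha, effect size or rating distribution for CGI-I, so there is no figure of the plan's to reproduce.

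**Step 1: coefficients.** With I intercepts, the count is I + 1 (treatment) + (V - 1) + (V - 1). The nominal form repeats the one-intercept set for each of six contrasts. There is no baseline term, because CGI-I has no baseline value.

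| Form | Cohorts 1-5 | Cohort 6 |
|---|---|---|
| Binary | 1+1+6+6 = 14 | 1+1+8+8 = 18 |
| Cumulative logit | 6+1+6+6 = 19 | 6+1+8+8 = 23 |
| Nominal | 6 × 14 = 84 | 6 × 18 = 108 |

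An unstructured working correlation adds at least one term per visit pair: 7 × 6 / 2 = 21, or 9 × 8 / 2 = 36. A robust covariance sums one contribution per woman, so its rank cannot exceed the number of women. Twelve women fall short of every form in the table. Twenty just exceed 19. No cohort of up to 30 reaches 84.

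**Step 2: how fits behave.** Sixty data sets per size were simulated from an assumed latent model over 7 visits, with a binary GEE and independence working structure. A usable fit (all coefficients below 12 on the logit scale) was obtained in 7 of 60 with 10 women, 10 with 12, 39 with 20 and 53 with 30. Among usable fits, the robust covariance had rank at most 8 of 14 with 10 women and at most 10 of 14 with 12.

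**Step 3: sparsity.** A 2×7 table has 14 cells, so the mean count is 10/14 = 0.7 to 30/14 = 2.1. In simulation 88-100% of cells had an expected count below 5.

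**Step 4: power of the asymptotic tests.** Assumed: two-sided 0.05; placebo ratings 10/20/30/25/10/4/1% for levels 1 to 7; common odds ratio (OR) towards better ratings; 4,000 trials; Wilcoxon with tie and continuity corrections.

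| OR | Per arm | Chi-square | Wilcoxon | Ratio |
|---|---|---|---|---|
| 5 | 5 | 6% | 20% | 0.30 |
| 5 | 10 | 18% | 45% | 0.40 |
| 5 | 15 | 34% | 66% | 0.52 |
| 8 | 10 | 33% | 65% | 0.51 |

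With a bell-shaped placebo distribution and no continuity correction, OR 4 gives 0.04/0.20 = 0.20 at 5 per arm, 0.11/0.37 = 0.30 at 10 and 0.20/0.53 = 0.38 at 15. OR 10 gives 0.11/0.41 = 0.27, 0.36/0.75 = 0.48 and 0.62/0.91 = 0.68.

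**Step 5: exact versions.** Over 120 scenarios (six placebo distributions, OR 2, 3, 4, 6 and 10, and 5, 6, 10 or 15 per arm), the Fisher-Freeman-Halton test had median ratios to exact Wilcoxon of 0.55-0.68 by arm size. Permutation versions with the Step 4 distribution gave 0.50-0.71. When only three levels occur, the gap is small: OR 4 with 10 per arm gives 0.227/0.275 = 0.83.

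**Step 6: source of the loss.** At equal noncentrality, a 6-df chi-square test keeps 0.50-0.74 of the 1-df power when the latter is 20-90%. The rest comes from Pearson being conservative in sparse tables: with the Step 4 placebo distribution, null rejection was 1.9-2.6%, against 3.1-5.5% for Wilcoxon.

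**Step 7: a different effect shape.** Assume placebo 5/15/30/30/12/6/2% and a bimodal ganaxolone response 40/10/10/15/13/8/4%. Chi-square then does better at 10 per arm (0.254/0.161 = 1.58) and at 15 (0.444/0.209 = 2.12).

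**The case against.** A reader might infer that the SAP sends CGI-I to a chi-square test and so more than halves power in most situations. The documents do not support that. Chi-square is an example, available only if the GEE does not converge and alongside other covariance structures. A rank test already fits under alternative methods, and a cumulative-logit GEE, which uses the order, is not excluded.

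The halving is not general either. In the 120 scenarios the Pearson ratio fell below one half in 77, but in only 13 of 30 at 15 per arm and in 5 of 40 when ratings use three or four levels. With exact tests it fell below one half in 19. A one-direction proportional-odds shift is also the pattern that suits Wilcoxon best.

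Other fair points stand:
- A rank-deficient robust covariance blocks a full joint test but not a single treatment contrast at one visit. In a simulated binary fit with 10 women, every such contrast had a finite, positive standard error.
- It would be wrong to say that the fallback discards most of the evidence. Category frequencies, percentages and bar charts are shown whatever test is used.
- SAP 6.2, 12.0 and 12.5 disclaim power and formal testing, and SAP 12.5.1 makes the HAMD17 mean difference the most influential outcome.
- SAP 12.5.3 carries no text in the public copy, so other CGI-I analyses may exist.

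These points limit the size of the problem. They do not supply the model form or an order-using fallback. Fisher's exact test repairs the approximation but still ignores order; it appears only in the protocol, whose statistical section SAP 4.0 says it supersedes.

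**Conclusion.** The concern holds in limited form. The SAP leaves the CGI-I model form open, with 19 or 23 coefficients at the least for an ordinal fit to the full rating and 84 or 108 for a nominal one, against about 10-30 women. Failure or unreliable standard errors are foreseeable in the smaller cohorts, and every test named for that case ignores order.

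Under a one-direction shift over all seven levels, Pearson chi-square keeps roughly one third to one half of Wilcoxon power at 5-15 per arm, and 0.20-0.68 across the bell-shaped scenarios shown. Exact versions keep about 50-70%. These figures rest on assumed distributions, odds ratios and alpha. With few levels in use the difference is minor, and with a bimodal effect it can reverse.

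Because the p-values are declared aids to interpretation, this is a cheap improvement and not a threat to the trial's main conclusion.

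**What to change.** In SAP 12.5:
- State that any GEE for CGI-I is a cumulative-logit (ordinal) model.
- Replace chi-square as the CGI-I fallback with an exact Wilcoxon-Mann-Whitney test by visit, at least at +60h for Cohorts 1-5 and Day 29 for Cohort 6. Report with it the probability that a ganaxolone woman has the better rating.
- Keep chi-square or Fisher's exact test for the binary HAMD17 response and remission endpoints.

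The cost is a few lines of SAP text and one simple program, with no new data. The downside is small: the fallback has no longitudinal model, so the linked imputation sensitivity analysis does not carry over to it, and it is less sensitive to non-monotone effects. The category frequencies already planned would still show such effects.
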